- Evidence of pregnancy
- Any infection that is opportunistic, such as active TB and other infections whose nature or course may suggest an immuno-compromised status
- Severe laboratory abnormalities:
 - Neutrophil count $\leq 0.5 \times 10^3/\mu\text{L}$
 - Platelet count $\leq 50 \times 10^3/\mu\text{L}$

- Alanine aminotransferase (ALT) and/or aspartate aminotransferase (AST) values >3x upper limit of normal (ULN) with total bilirubin >2x ULN (unless elevated bilirubin is related to confirmed Gilbert's Syndrome)
- Confirmed AST and/or ALT >5 x ULN (for more than 2 weeks)
- Treatment with any prohibited concomitant medication or procedure
- Other reasons that may lead to the permanent discontinuation of study drug include certain AEs deemed related to the study drug.

Study drug dosing may be temporarily suspended in the event of:

- Clinically important laboratory abnormalities, such as:
 - Neutrophil count $\leq 1.0 \times 10^3/\mu\text{L}$ but $>0.5 \times 10^3/\mu\text{L}$
 - Platelet count $\leq 100 \times 10^3/\mu\text{L}$ but $>50 \times 10^3/\mu\text{L}$
 - Creatine phosphokinase (CPK) >10x ULN
- Other intercurrent illnesses or major surgery
- An infection that requires systemic treatment with antibiotic, antifungal, antiviral, anti-parasitic, or anti-protozoal agents or requires oral treatment with such agents for longer than 2 weeks
- Treatment with systemic corticosteroids or non-steroidal immunosuppressive/immunomodulating medications (eg, cyclosporine, methotrexate, azathioprine, mycophenolate-mofetil, Janus kinase inhibitors, biologic agents, etc).

Duration of study drug suspension should be reviewed on a case by case basis and can be discussed among the PIs.

Unblinding

In case of an emergency, when knowledge of the test article assignment is required for the medical management of an individual subject, the subject will be unblinded. The code should be broken only in the event of a medical emergency, when knowing the treatment assignment is absolutely necessary. The investigators will notify the IRB, FDA and any other regulatory group, within 24 hours after determining that it is necessary to unblind the treatment assignment. The investigator must also indicate in source documents and in the CRF that the blind was broken and provide the date, time, and reason for breaking the blind. Any AE or SAE associated with breaking the blind must be recorded and reported as specified in this protocol.

A clinical data manager will assemble all the patient data by groups (treatment versus placebo) and the biostatistician may request the unblinding of subject treatment assignment for analyzing safety data, upon the appearance of unequal adverse events.

Safety Evaluation

This is a phase II study. Safety and tolerability will be evaluated from the AEs, physical examinations, vital sign measurements, and clinical laboratory test results. More frequent safety evaluations may be performed if clinically indicated or at the discretion of the investigator.

Aggregated AEs will be evaluated monthly by the PI/research teams.

Safety data will be reviewed by the investigators, study teams, biostatisticians, who will monitor the study on a regular basis and meet regularly (approximately every 3 months, depending on the number of subjects enrolled). The local IRBs and FDA will be notified of adverse events (as required by each institution).

Physical Examination/Vital Signs

A licensed physician, physician assistant, nurse practitioner, or registered nurse will perform physical examinations at the time of screening. Body weight (kg), height (cm), blood pressure, and heart rate will be measured at screening. At all other visits, only blood pressure and heart rate will be measured.

Physical examination consists of assessments of general appearance; skin; head, eyes, ears, nose, and throat (HEENT); heart; lungs; abdomen; extremities; neurological function; and lymph nodes.

Safety Laboratory Determinations

Laboratory evaluations will be performed according to the flowchart on page by a CLIA certified laboratory at the study site. All laboratory tests with clinically important abnormal results identified after test article administration will be repeated until the values return to normal, baseline or non-clinically significant, as appropriate. Each abnormal lab will be indicated as clinically significant or not clinical significant.

Biopsy Site Wound Infections

If a wound infection occurs at the site of the biopsy, the site will perform a bacterial culture as part of standard of care procedures.

MEASURES TO MINIMIZE/AVOID BIAS:

Subject Identification

Subjects are numbered sequentially. Each subject will be assigned a unique number and will keep this number for the duration of the study. Subject numbers will not be reassigned or reused for any reason. Subjects who discontinue or withdraw from the study before receiving a treatment assignment code, who re-enroll at a later time must be assigned a new subject number. Subjects should be identified only by their assigned identified code number. The investigator must maintain a subject master log linking the subject number to the subject's name. The investigator must follow all applicable privacy laws in order to protect a subject's privacy and confidentiality.

Randomization and Blinding

A subject who meets all of the inclusion and exclusion criteria will be assigned a randomization number pre-dose on day 0/baseline. The randomization number is distinct from the subject number.

After fulfilling the enrollment criteria, the subjects enrolled will be randomized in a 2:1 ratio of dupilumab to placebo.

The randomization for both sites will be performed by the designated Research Pharmacist/personnel at the Icahn School of Medicine utilizing the Web site <http://www.randomization.com> (or similar). The method uses random block sizes and randomly permuted blocks.

Approximately 60 subjects will be enrolled in the study in order to have at least 54 subjects complete (taking into account a 10% drop out rate). Subjects will be assigned a randomization number on day 0/Baseline. The randomization schema will be kept confidentially after generation.

INVESTIGATIONAL DRUG SUPPLY AND BLINDING:

Regeneron Pharmaceuticals will provide dupilumab 300 mg for 40 subjects in Phase I and for all 60 subjects during Phase II (a total of 25 doses in Phase I to those 40 subjects randomized to receive dupilumab, followed by another 24 doses in Phase II; a total of 24 doses in Phase II to the 20 subjects who received placebo in Phase I).

Eligible patients will receive a 600 mg SC dupilumab loading dose (300 mg initial dose, followed by a 300 mg loading dose) on day 0/Baseline, and then continue with 300 mg SC dupilumab once weekly starting on day 8. At Week 24, subjects previously on dupilumab will receive 1 injection of 300 mg dupilumab and 1 injection of placebo to maintain the blind of the study; subjects previously on placebo will receive 2 injections of 300 mg dupilumab. All subjects should be observed for 30 minutes following the injections at Baseline and at Week 24.

Matching placebo prefilled syringes (that will appear identical to the dupilumab syringes) will be provided by the company to the study sites. The subjects and the staff will remain unaware of the individual treatment assignment during the study. All study medication will be stored in a secure cool area between 2-8°C. Study drug will be administered to subjects at each study visit, with subsequent weekly injections performed by the patients at home. Patients (and/or caregivers) who are willing and able to administer dupilumab outside of the clinic will be trained on injecting study drug during the initial clinic visit.

We will query the subjects during each study visit on any missed injections and document this information. The investigative sites will account for all study drug dispensed and stored during the study.

STATISTICAL CONSIDERATIONS:

Sample Size Calculation

The primary outcome for this study is the SALT change at week 24. For patients with similar disease severity, a change in SALT of less than 5 units was observed ([name] et al, 2019). Assuming that dupilumab will induce a change in SALT of at least 25 units with a standard deviation of 10 at week 24, a sample size of 54 completed patients randomized 2:1 treatment to placebo (i.e. 36 in the treatment arm, 18 in the placebo arm) will provide 97% power to detect differences with Placebo based on a two-sided Student's t-test with a 0.05 type I error. Assuming that 10% of patients drop out of the study, we plan to enroll 60 total patients (i.e. 36 in the treatment arm, 18 in the placebo arm).

Demographics and Other Baseline Characteristics

Descriptive statistics of demographics and other baseline characteristics will be presented for all subjects and tabulated by treatment group. Presentations of age, sex, ethnicity, race and baseline will also be given. Other baseline characteristics include height, weight, and vital signs, duration of the AA and AD, concurrent diagnoses from medical history and indications for concomitant medication, concomitant medication, and previous AA and AD treatments.

Analysis of Primary Endpoint

A Mixed effect Model Repeated Measurement (MMRM) will be used to detect any overall differences in the treatment effect at week 24 compared to baseline.

Analysis of Secondary Endpoints

A Mixed effect Model Repeated Measurement (MMRM) will be used to detect any overall differences in the treatment effect at week 48 compared to baseline, as well as at week 48 compared to week 24. This formulation intrinsically models the within patient correlation structure as in the case of a paired t-test. This approach introduces less bias than restricting the analysis for those patients who completed the study. A similar model will be used to evaluate the change in eyelashes and eyebrows scores, as well as in Eczema Area and Severity Index (EASI) at each visit compared to baseline.

A two-sided Fisher exact test will be used to compare the percentage of patients who achieve 50% improvement in SALT, eyelashes, eyebrows and EASI scores (calculated as $100 \times (\text{SCORE}_{\text{baseline}} - \text{SCORE}_{\text{W24}}) / \text{SCORE}_{\text{baseline}}$) between drug and placebo groups. The same approach will be used for other discrete variables, SALT-75, and SALT-90 at each visit compared to baseline.

Analysis of Exploratory Endpoints

The change from Baseline in molecular markers in skin biopsies after treatment will be analyzed using a mixed effect linear model with treatment and time interaction as a fixed effect and a random effect for each patient. This formulation intrinsically models the within patient correlation structure as in the case of a paired t-test, and introduces less bias than restricting the analysis for those patients who completed the study.

Analysis of Mechanistic Endpoints

For comparison of expression levels of lesional, and non-lesional AA skin, we will use RT-PCR by Taqman Low-density arrays and RNA-sequencing. RT-PCR values will be normalized to the housekeeping gene RPLP0 (validated in our AD and AA studies) and log-2 transformed prior to analysis. RNA-sequencing data will be pre-processed using standard pipeline (exhaustively used by our group in a large number of studies) and log-2 voom-transformed expression. Mixed effect model will be used and p-values for the moderated t-tests and paired-t-test will be adjusted by Benjamini-Hochberg procedure.

Extensive bioinformatics tools will be employed to gain insights into the results and test hypotheses that are generated in the “data mining stage”. This will include (but will not be limited to) pathway and gene-set enrichment analyses using Ingenuity software, GSEA, the R package GSVA (Gene Set Variation Analysis) and other in-house codes produced

by our group. To define cellular and molecular biomarkers of AA in skin biopsies, biomarkers will be divided into those that show significant group differences and those that do not. Multiple regression models will be used to determine the best set of biomarkers that predict disease activity and response.

Gene expression changes in hair keratins and the immune axes (Th1, Th2, Th17, Th22) will be jointly correlated with clinical responses by multivariate analysis using multivariate u-statistics and R package muStat, as previously reported [43].

Data Transfer and Management

Data including the patient info, demographics, clinical scores and treatment allocation code will be sent to our Biostatistical Team in password-protected files.

Data from the [name] Lab (where all mechanistic blood and skin studies will be done), including FASTQ files, real-time PCR (RT-PCR), and serum proteomics will be deposited in the Mount Sinai Box and Amazon S3 bucket, having the necessary safeguards for protection of human subjects research. [name] lab members will not have access to the treatment code until all lab work has been completed and the data transferred to our Biostatistical Team.

All data management steps taken to reformat and merge the clinical and laboratory data will be carried out using R codes, so all the steps of the processes can be reproduced.

Management of the Analysis

Analysis of RT-PCR and RNA-sequencing will all be conducted using R language and bioconductor packages. Codes will be QC-ed by at least one independent member of the Biostatistical Team, other than the member who coded the analysis.

Analysis will be run in our desktops, with a backed up copy in the Mount Sinai Box. Analysis results will be shared with the study teams of Drs. [name], [name], and [name], as well as [name] who holds joint appointments at Rockefeller University and Mount Sinai, and [name] who is our study consultant, via the Mount Sinai Box. Once the analysis is finalized, all data will be deposited in [name] and [name] central file storage system (CFS), which is accessible to all research members. Both Mount Sinai Box and the CFS have backup capabilities and are encrypted and password protected. Access to the Mount Sinai Box specific for the project will be shared with the Rockefeller team and [name].

Analysis of Safety and Tolerability

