The immunopathogenesis of AA is poorly understood. While previous studies have primarily focused on the role of Th1 in AA [26], there is increasing evidence for the role of the Th2 axis in this disease. First, AD is the strongest risk factor for AA, and the two diseases commonly co-occur in patients [27]. In a study of more than 3500 AA patients, atopy (e.g. allergic rhinitis, asthma, and/or eczema) was the most common comorbidity, affecting more than 38.2% of AA patients [28]. Second, several studies have reported high levels of Th2 cytokines (e.g. IL-4, IL-5, IL-10) in the skin [27] and the serum of AA patients [29], as well as eosinophilia and elevated IgE levels in the blood [30-32]. Finally, genetic studies in AA have identified polymorphisms in filaggrin, IL-4, and IL-13 [28, 33]. Filaggrin mutations are associated with a more severe AA phenotype [33], and IL-13 is a known susceptibility locus for other autoimmune conditions, including atopy [34]. These findings provide strong biologic and genetic evidence for the observed relationship between AA and AD, and the possible pathogenic role of the Th2 axis in AA.

Our recent data from a cohort of 27 AA patients ranging from mild to severe (total body hair loss) suggest that similar to psoriasis and AD, AA is a highly inflammatory disease with robust activation of Th1, Th2, and IL-23 (both p19 and p40 subunits) cytokine pathways (**Figure 1**) [35]. Using RT-PCR, we showed that the IL-13 cytokine showed the highest increases in gene expression in lesional AA scalp compared to non-lesional AA scalp. Significant down-regulation of hair-associated keratins was also observed and is a hallmark of AA (**Figure 2**). Finally, we found that lesional scalp of patients with extensive AA involvement is associated with greater immune and keratin dysregulation compared with that of patients with limited disease. Importantly, patients with and without concurrent AD were shown to have a similar AA scalp phenotype, and similar activation of the Th2 pathway [35].

[figure not shown]
Th1/IFN

Th2

T Cell Activation

IL-23

[figure not shown]
[figure not shown]

[figure not shown]

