Figure 1. Alopecia areata (AA) scalp lesions are characterized by up-regulation of Th1 (IFN γ , CXCL9, CXCL10), Th2 (IL-13, CCL5, CCL18), and T cell activation (IL-2, IL-2RA, IL-15) related products as well as IL-23 (p19 and p40) cytokine. Real-time (RT)-PCR comparisons of inflammatory markers in lesional (LS), non-lesional (NL), and healthy scalp and skin samples from patients with alopecia areata (AA), atopic dermatitis (AD), or psoriasis (PsO) and normal skin from

healthy subjects. Expressions are normalized to hARP (Human acidic ribosomal protein). Mean (\log_2 expression/hARP) \pm SEM. *P < .05, **P < .01, and ***P < .001.

Early Keratins:

Middle Keratins:

Late Keratins:

[figure not shown]

Figure 2. Early, mid, and late hair keratins in normal scalp as compared to lesional and non-lesional scalp of alopecia areata (AA) patients. The mRNA expressions of hair keratins in LS and NL AA scalp were compared to normal scalp by RT-PCR. hARP/human acidic ribosomal protein. Mean (\log_2 expression/hARP) \pm SEM. *p-value <0.05; **p<0.01; ***p<0.001. LS/Lesional, NL/non-lesional.

We also recently treated 3 patients with moderate-to-severe AA with ustekinumab, an anti-IL12/IL-23p40 inhibitor, and followed clinical responses with mechanistic studies in pre- and post-treatment scalp biopsies after 16 weeks of therapy [36]. Interestingly, although ustekinumab blocks the IL-12/IL-23 cytokines, the highest and most significant reductions coupled with successful hair regrowth were seen in the Th2 cytokines, including CCL13, CCL18, and CCL26, that are also highly up-regulated in AD and go down with dupilumab according to prior studies [37]. Interestingly, the suppression of the Th2 axis with ustekinumab was more consistent and significant than that of interferon/Th1 genes. We also observed suppression of T-cell and dendritic cell genes. This series is the first report to link targeted immune antagonism to clinical and molecular AA reversal, including suppression of immune markers and up-regulation of hair keratin genes.

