- AD Clinical assessments, if applicable (EASI, IGA, SCORAD)
- Dispense/administer study drug
- Record concomitant medications and adverse events

Visit 5 – Week 12

- Urine pregnancy test for all female subjects of child-bearing potential to confirm subject is not pregnant
- Obtain vital signs
- AA Clinical assessments (SALT, aaPGA, and eyebrow/eyelash)
- AD Clinical assessments, if applicable (EASI, IGA, SCORAD)
- Questionnaires (AASIS and AA-QLI)
- Standardized photographs
- Obtain CBC, CMP, LDH, CRP, and Total serum IgE
- Collect blood sample for mechanistic endpoints
- Perform biopsy of lesional skin of the scalp
- Dispense/administer study drug
- Record concomitant medications and adverse events

Visit 6 – Week 16

- Urine pregnancy test for all female subjects of child-bearing potential to confirm subject is not pregnant
- Obtain vital signs
- AA Clinical assessments (SALT, aaPGA, and eyebrow/eyelash)
- AD Clinical assessments, if applicable (EASI, IGA, SCORAD)
- Standardized photographs
- Dispense/administer study drug
- Record concomitant medications and adverse events

Visit 7 – Week 20

- Urine pregnancy test for all female subjects of child-bearing potential to confirm subject is not pregnant
- Obtain vital signs
- AA Clinical assessments (SALT, aaPGA, and eyebrow/eyelash)
- AD Clinical assessments, if applicable (EASI, IGA, SCORAD)
- Standardized photographs
- Dispense/administer study drug
- Record concomitant medications and adverse events

Visit 8 – Study Cross Over (Week 24)

- Urine pregnancy test for all female subjects of child-bearing potential to confirm subject is not pregnant
- Obtain vital signs
- AA Clinical assessments (SALT, aaPGA, and eyebrow/eyelash)
- AD Clinical assessments, if applicable (EASI, IGA, SCORAD)
- Questionnaires (AASIS and AA-QLI)
- Standardized photographs
- Obtain CBC, CMP, LDH, CRP, and Total serum IgE
- Collect blood sample for mechanistic endpoints
- Perform biopsy of lesional skin of the scalp

- Perform a biopsy of lesional skin for subjects with a concomitant history of atopic dermatitis and active AD lesions if present; if no active AD lesions, biopsy of skin will be collected near biopsy performed at Baseline

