- Urine pregnancy test for all female subjects of child-bearing potential to confirm subject is not pregnant
- Obtain vital signs
- AA Clinical assessments (SALT, aaPGA, and eyebrow/eyelash)
- AD Clinical assessments, if applicable (EASI, IGA, SCORAD)
- Questionnaires (AASIS and AA-QLI)
- Standardized photographs
- Obtain CBC, CMP, LDH, CRP, and Total serum IgE
- Collect blood sample for mechanistic endpoints
- Record concomitant medications and adverse events
- Obtain **optional** biopsy of lesional scalp
- Obtain **optional** biopsy of lesional skin for subjects with a concomitant history of atopic dermatitis

Visit 15 – Week 60

- Urine pregnancy test for all female subjects of child-bearing potential to confirm subject is not pregnant
- Obtain vital signs
- AA Clinical assessments (SALT, aaPGA, and eyebrow/eyelash)
- AD Clinical assessments, if applicable (EASI, IGA, SCORAD)
- Record concomitant medications and adverse events

Visit 16 – Week 72

- Obtain vital signs
- AA Clinical assessments (SALT, aaPGA, and eyebrow/eyelash)
- AD Clinical assessments, if applicable (EASI, IGA, SCORAD)

- Questionnaires (AASIS and AA-QLI)
- Standardized photographs
- Record concomitant medications and adverse events

LABORATORY TESTING:

Each site may utilize their own local lab for CBC, CMP, LDH, CRP, IgE, HIV, HBV, HCV, Quantiferon Gold, and pregnancy testing. Lab certifications for any lab used should be kept in the study binder. RU will have to transport biopsy samples as well as blood samples for mechanistic testing (and potentially IgE testing) to Mount Sinai via proper and documented means.

SAFETY MONITORING:

The study will be conducted in accordance with our department's Standard Operating Procedures, which are based on US FDA Title 21 Code of Federal Regulations and ICH Good Clinical Practice guidelines. An investigator will review all laboratory results and assess for adverse events. The principal investigator will be informed of all adverse events. In the event that a subject's safety is compromised, the investigator will discontinue the subject immediately.

STUDY WITHDRAWAL:

In the event a study subject wants to withdraw early from the study or the subject is being discontinued from the study for any reason, the following procedures should be followed:

- Urine pregnancy test for all female subjects of child-bearing potential to confirm subject is not pregnant
- Obtain vital signs
- Obtain CBC, CMP, LDH, CRP, and Total serum IgE

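### Post-Screening total serum IgE is reported unmasked on the routine laboratory panel in the blinded phase, so the Week 12 value could hint at assignment before SALT is scored at Weeks 16, 20 and 24

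*Combined protocol and SAP*

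**What the plan says.** **Schedule.** The Week 12 visit list reads "Obtain CBC, CMP, LDH, CRP, and Total serum IgE". Table 1 shows total serum IgE at Screening, Weeks 12, 24, 36 and 48, and Early Termination.

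**Where it is run.** Laboratory Testing: "Each site may utilize their own local lab for CBC, CMP, LDH, CRP, IgE, HIV, HBV, HCV, Quantiferon Gold, and pregnancy testing". The same section foresees the Rockefeller site sending "blood samples for mechanistic testing (and potentially IgE testing) to Mount Sinai".

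**Who reads it.** Safety Monitoring: "An investigator will review all laboratory results and assess for adverse events". Safety Laboratory Determinations adds: "Each abnormal lab will be indicated as clinically significant or not clinical significant". Neither makes an exception for IgE.

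**What a reader would make of it.** The background lists evidence for the Th2 axis in alopecia areata, "as well as eosinophilia and elevated IgE levels in the blood". Describing the ustekinumab series, it says of Th2 products including CCL13, CCL18 and CCL26 "that are also highly up-regulated in AD and go down with dupilumab according to prior studies".

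**Blinding.** Investigational Drug Supply and Blinding: "The subjects and the staff will remain unaware of the individual treatment assignment during the study". That section does not mention laboratory results. Data Transfer and Management withholds the treatment code from the mechanistic laboratory until its work is complete, but sets no rule on results that go to the sites.

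**Who scores.** Procedures assigns clinical assessments to trained assessors and suggests the same assessor for a given subject. It does not say whether they may see laboratory reports.

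**The concern.** The primary outcome is the change in SALT at Week 24, and SALT is built from visual estimates of percentage hair loss. The plan protects the blind with matching syringes, a placebo injection at Week 24 for subjects already on dupilumab, and 30 minutes of observation for everyone. It leaves open a laboratory result that its own background ties to the pathway under study.

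An investigator who believes that background and sees IgE drop between Screening and Week 12 may form a view about assignment. If that person also scores SALT, or talks to the assessor, the view could colour SALT, eyebrow/eyelash and aaPGA scores at Weeks 16, 20 and 24, and judgements on whether adverse events are drug-related. The suggestion to keep one assessor per subject would carry the view from visit to visit. A shift toward the expected result would favour dupilumab.

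**Working it through.** **1. Which values can matter for the primary endpoint.** Screening is the only pre-dose IgE in the visit lists and Table 1. Week 12 is the only later sample whose result can be known before the Week 24 SALT, because the Week 24 sample is drawn at that same visit. The relevant signal is the change from Screening to Week 12. The reporting time is not stated; being known before Week 16 is an inference.

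**2. Whether a safety rule needs the value.**

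| Rule | Laboratory inputs named |
|---|---|
| Inclusion criterion 8 | White cells, platelets, creatinine, AST/ALT, bilirubin, hemoglobin |
| Permanent discontinuation | Neutrophils, platelets, ALT/AST, bilirubin |
| Temporary suspension | Neutrophils, platelets, CPK |

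IgE is in none of them. The general duties to repeat clinically important abnormal tests and to grade each abnormal value could still apply to it.

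**3. How much one IgE result could tell a reader (illustration).** The documents give no IgE effect, so every input except the allocation ratio is assumed:
- log change Screening to Week 12 is normal, with mean 0 on placebo and ln(1 − f) on dupilumab;
- f = 20%, 40% or 60%; the SD of the log change is 0.3 or 0.5 in both arms;
- prior probability of dupilumab is 2/3, from the 2:1 randomization.

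Let d = −ln(1 − f)/SD. The guess that is right most often uses the 2:1 prior, and its accuracy is

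(2/3)·Φ(d/2 + ln 2/d) + (1/3)·Φ(d/2 − ln 2/d).

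Worked case, f = 40%, SD 0.3: d = 0.5108/0.3 = 1.703; d/2 = 0.851; ln 2/d = 0.407. Accuracy = (2/3)·Φ(1.258) + (1/3)·Φ(0.444) = (2/3)(0.896) + (1/3)(0.672) = 0.82.

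| Fall on drug | SD 0.3 | SD 0.5 |
|---|---|---|
| 0% | 67% | 67% |
| 20% | 70% | 67% |
| 40% | 82% | 73% |
| 60% | 94% | 84% |

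The benchmark is 67%, not 50%: calling every patient dupilumab is already right in two of three cases. At a 20% fall the gain is 3 points or less; at 60% it is 17 to 27 points.

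**4. What a guess could do to the test (second illustration).** Assume no true effect, 36 versus 18 completers, a two-sided t-test at 0.05, and an assessor who scores b SALT units more improvement when the guess is dupilumab than when it is placebo. For simplicity the guess here uses the midpoint between the arms, so it is right with probability p = Φ(s/2) in either arm when IgE change separates the arms by s SDs. The mean bias is b(2p − 1) and the variance per patient is SD² + b²p(1 − p).

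| s | p | b | Mean bias | Rejection rate, SALT SD 10 | Rejection rate, SALT SD 17.5 |
|---|---|---|---|---|---|
| 1 | 0.69 | 2 | 0.8 | 6% | 5% |
| 1 | 0.69 | 5 | 1.9 | 10% | 7% |
| 2 | 0.84 | 2 | 1.4 | 7.5% | 6% |
| 2 | 0.84 | 5 | 3.4 | 21% | 10% |

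SD 10 is the plan's figure; 17.5 is a wider alternative. Both s and b are assumptions. With s = 0 the bias is 0 and the rate is 5%.

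**The case against.** The strongest reply is that the central premise is not in the documents. The statement about markers falling with dupilumab concerns Th2 chemokines in a discussion of scalp biopsies, not serum IgE. The background says only that elevated IgE has been reported in the blood of patients with alopecia areata. A reader might infer that IgE falls on dupilumab by Week 12 and so reveals assignment; the documents do not say that it falls, by how much, or when. This stands, and it limits the point to a possible route.

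Second, the path to the scorer is inferred. Sites may, not must, use a local laboratory; an investigator reads results while trained assessors score; and staff are to remain unaware of assignment. This also stands as a limit. But the duties to review all results and grade each abnormal one cannot be met unless someone on the study sees IgE, and the plan neither masks the value nor separates the two roles.

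Third, masking IgE leaves other cues. The background names eosinophilia beside IgE, and the CBC differential stays open. In subjects with active atopic dermatitis, EASI and IGA are scored at the same visits as SALT. The benefit of masking IgE alone is therefore partial. The CBC, however, feeds named safety rules, and IgE does not.

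Fourth, scale: even 3.4 SALT units is small beside the planned difference of about 20 (25 minus 5). This is fair if the true effect is that large. It reassures less if the effect is small or absent, where the rejection rate matters.

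**Conclusion.** The point holds as a gap in the blinding plan. As written, a Week 12 IgE result can reach an investigator during the blinded phase, that person may also be the SALT assessor, and no named safety rule depends on the value. The documents support saying that IgE could hint at assignment; they do not support saying that it does.

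The size is unknown. Under the stated assumptions, the best single-patient guess ranges from no better than 67% to 94% correct. Any effect on the Week 24 comparison also needs an assessor who has the result and lets it influence the score. A reader might also infer that the Week 24 SALT is compromised or that the plan's power is affected; nothing in the documents shows either. The case for acting is that the outcome is visual and the remedy is cheap.

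**What to change.** In Laboratory Testing and Safety Monitoring, state that post-Screening total IgE results are withheld from investigators, efficacy assessors and subjects until the blind is lifted, and are sent only to the biostatistical team. Name a reviewer already on the study, who does no efficacy assessment, to check any abnormal IgE value, so that the general duties on abnormal results are still met. CBC, CMP, LDH and CRP stay open for safety review.

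Sending samples to Mount Sinai is not enough by itself, because Mount Sinai is a study site; the withholding instruction is what masks the result.

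The cost is a short protocol addition, a separate reporting route for one analyte, and a small task for the named reviewer. No named entry, stopping or suspension rule loses an input. The risk is reduced, not removed, because eosinophils in the CBC differential remain visible.
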